4.2 Efficacy analysis

The *FA subject sample* will be used for the analysis of the efficacy data. Additionally, primary efficacy results analysis will be conducted on the *PP sample* as the sensitivity analysis. Descriptive statistics will be presented by treatment arm and by stratification level (Age Category) for all planned efficacy endpoints.

All analyses will be based on available data only and no missing data will be imputed.

All parameters will be summarized using descriptive statistics and listed.

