Subjects will be treated with Racecadotril tid according to the body weight dose requirement on an in- or out-patient basis for maximum 5 days. One arm will be treated with ORS alone as standard treatment, the other treatment arm will be treated with ORS (according to the registered local label and the instruction of the investigator) in addition to Racecadotril. ORS will be prescribed by the investigator and will be taken according to the product label and the instruction of the investigator. The parent(s)/caregiver(s) will be instructed to stop study drug treatment when the patient recovered. On each day, the parent(s)/caregiver(s) will fill in their diaries, documenting the date and time of each individual stool, the stool consistency of each stool (diarrheal/watery or normal), the amount of ORS and the study drug intake. After the occurrence of two consecutive normal stools, the parent(s)/caregiver(s) can stop recording of the diary and

[figure not shown]
return to the study site for the end of treatment visit. The date of recovery is the day when the first of two consecutive normal stools were excreted. AEs are to be reported on an ongoing basis.

End of treatment (Day 6 or early recovery, Visit 2)

The last dose of study drug will be the morning dose of day 6, if not recovered earlier. The same day, or within 24 hours after recovery, the parent(s)/caregiver(s) will visit the site for the end of treatment visit of the child. Data on vital signs, AEs, physical examination and concomitant medication will be collected. Subjects will return their diaries and unused medication.

Safety follow-up

A phone call will be performed at 5-7 days after end of the treatment period for the safety follow-up.

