6 REMOVAL OF SUBJECTS FROM THERAPY OR ASSESSMENT

All subjects are free to withdraw from participation in this study at any time, for any reason, specified or unspecified, and without penalty or loss of benefits to which the subject is otherwise entitled.

The Study Termination form must be completed for all subjects who did not fail screening, those who completed and those who prematurely terminated the study.

In case of premature termination of the subject from the study, the primary reason for this premature termination is to be indicated according to the following definitions:

- Adverse event: discontinuation due to any adverse event (AE) with a corresponding entry reflected on the Adverse Events form in the CRF.
- Lack of efficacy: subject fails to respond to the study drug at an acceptable level where the subject or the Investigator feels it is in the best interests of the subject to seek another treatment.
- Lost to follow-up: the subject fails to return to the study site for scheduled visits and does not respond to telephone or written attempts to contact.
- Withdrew consent: subject decides to stop his/her participation in the study for any reason other than an AE, or is unable to complete the study as described in the clinical study protocol (e.g. subject is relocating to another location).
- Administrative: the Sponsor decides to discontinue the study (either at the study site or the entire study), e.g. general safety problems leading the Sponsor to entirely stop the study.
- Protocol violation – anything which is in direct violation of the clinical study protocol (e.g. inclusion/exclusion violation).

Subjects with two consecutive temperature measurements of > 39 degrees Celsius during the study should be withdrawn from the study for further diagnosis and alternative treatments. Also subjects whose disease state worsens, e.g. dehydration or increased vomiting, should be withdrawn from the study. An end of treatment visit will be performed.

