4.2.2 Secondary efficacy analysis

The secondary efficacy variables are

- Number of recovered subjects per treatment group in total and until each individual treatment day. Mean and median time until recovery per treatment group.
- Time until recovery, defined by date and time of the evacuation of the first of two consecutive normal stools.

Time until recovery, number of recovered subjects per treatment group in total and until each individual treatment day and mean and median time until recovery per treatment group will be estimated Kaplan Meier analysis as described for the primary endpoint.

- Global Physician Assessment at the end of treatment:
 - \circ 1 = Complete relief of acute diarrhea,
 - \circ 2 = marked improvement of acute diarrhea,
 - \circ 3 = moderate improvement of acute diarrhea,
 - 4 =slight improvement of acute diarrhea,
 - \circ 5 = no change in acute diarrhea,
 - \circ 6 = worsening of acute diarrhea.

Frequencies table will be performed for the Global Physician Assessment at the end of treatment by GPA score and by success rating. Treatment will be rated as success when the GPA score equals 1 or 2.

Description of the subgroup analysis is presented in the Section 4.2.3 of the SAP.

The comparisons of treatment arms using Fisher exact test will be performed by proportion of patients with Global Physician Assessment success at the end of treatment.

SAS code for the analysis:

PROC FREQ DATA = [dataset name]; WEIGHT [GPA frequency] / ZEROS; TABLES [GPA yes/no level] * [Arm] / EXACT FISHER;

RUN;

If SAS code produces the "Row or column sum zero. No statistics computed for this table." output due to insufficient memory available to complete the Fisher exact computations, then the p-value should be assumed as equal 1.0000.

• For toilet trained children and adolescents: number of stools per day as well as number of watery stools per day from start of treatment and until end of study treatment.

Number of stools and number of watery stools will be presented descriptively per treatment group and cumulatively until each day of treatment.

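### Children with no end-of-treatment Global Physician Assessment drop out of the success comparison, even when they left as treatment failures, so this secondary result can be biased

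*SAP*

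**What the plan says.** SAP 4.2 names the FA sample for efficacy and sets one missing-data rule: "All analyses will be based on available data only and no missing data will be imputed". SAP 4.2.2 defines the endpoint, "Treatment will be rated as success when the GPA score equals 1 or 2", and plans a formal between-arm test, "using Fisher exact test will be performed by proportion of patients with Global Physician Assessment success at the end of treatment". SAP 4.2.3 repeats the test by age subgroup. The SAS shell takes cell counts of yes and no ("WEIGHT [GPA frequency] / ZEROS") and mentions no category for a missing score. Protocol 10.1 makes subjects with non-missing data the default denominator for qualitative variables.

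On early leavers, Protocol 6 lists the reasons for premature termination, among them "Lack of efficacy: subject fails to respond to the study drug at an acceptable level". Protocol 7.7 withdraws children who need a prohibited medication. After the paragraph on fever and worsening disease, Protocol 6 adds "An end of treatment visit will be performed". The sentence listing what is collected at Visit 2 (Protocol 4.1) reads "Data on vital signs, AEs, physical examination and concomitant medication will be collected" and does not name the GPA. Neither do the flow charts or the visit table in SAP 6.1.4.

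**The concern.** A child who leaves to seek other treatment, or who needs an excluded antidiarrheal, has failed treatment in the ordinary sense. If no GPA was scored, the available-data rule removes that child from the comparison instead of counting a failure. The control arm is ORS alone and everyone knows the allocation, so the decision to leave can depend on both outcome and arm. The success rate rises in any arm that loses failures. If the arms lose different numbers, the test compares groups partly selected by outcome, and a real difference can be masked or an apparent one produced. Nothing else in the plan corrects this. The protocol's last-non-missing-value convention cannot help an item scored once, and the per-protocol sensitivity analysis covers only the primary endpoint.

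**Working it through.** **What the documents supply.** No GPA success rate, missing count or power figure is given, so there is no GPA figure of the plan's to reproduce. Two inputs come from Protocol 10.8: 62 per group, which is 55/(1 − 0.10) = 61.1 rounded up, and the 10% drop-out behind it (10% of 124 is about 12 children).

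**What is assumed.** All GPA rates, the missing counts, and that every missing score belongs to a non-success. For one scenario the rates are set near the 120-hour recovery rates in Protocol 10.8: 0.947 × 62 = 58.7, taken as 59, and 0.806 × 62 = 50.0, taken as 50. Recovery is a different endpoint and serves only as a plausible level.

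**Formula.** With s successes and m missing scores in an arm of 62, the plan's available-case rate is s/(62 − m). Counting missing as not a success gives s/62, wherever the missing scores fall. Tests are two-sided Fisher exact.

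| Successes (racecadotril, ORS) | Missing (racecadotril, ORS) | Available-case rates | Difference (points) | p |
|---|---|---|---|---|
| 59, 50 | 0, 0 | 95.2% v 80.6% | 14.5 | 0.025 |
| 59, 50 | 1, 6 | 59/61 = 96.7% v 50/56 = 89.3% | 7.4 | 0.15 |
| 52, 41 | 0, 0 | 83.9% v 66.1% | 17.7 | 0.037 |
| 52, 41 | 6, 6 | 92.9% v 73.2% | 19.6 | 0.010 |
| 52, 41 | 2, 10 | 86.7% v 78.8% | 7.8 | 0.32 |
| 52, 41 | 10, 2 | 100% v 68.3% | 31.7 | <0.0001 |
| 50, 50 | 6, 6 | 89.3% v 89.3% | 0 | 1.00 |
| 50, 50 | 3, 9 | 84.7% v 94.3% | −9.6 | 0.13 |
| 50, 50 | 2, 10 | 83.3% v 96.2% | −12.8 | 0.034 |

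The rates rise in every arm that has missing scores. The comparison moves little when losses are even. It shrinks when ORS loses more failures and grows when racecadotril does. Seven missing scores of 124 (5.6%) are enough to take the first scenario from p = 0.025 to p = 0.15. A false positive from equal arms needs a very uneven split: if 12 losses fell at random between arms, a split of 2/10 or worse has probability 2 × (1 + 12 + 66)/4096 = 0.039.

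**Bounds for the second row.** Taking the 7 missing scores in the way least favourable to racecadotril gives 59/62 v 56/62, p = 0.49. The most favourable way gives 60/62 v 50/62, p = 0.009.

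**Which denominator.** SAP 4.1 admits a child to the FA sample with any one post-baseline efficacy assessment, so diary data suffice. But diaries are handed in at Visit 2 (Protocol 4.1 and both flow charts). A child who never attends may have neither diary nor GPA and so fall outside the FA sample. An all-FA denominator would recover a child whose diary was returned or whose visit took place without a score, but not that one.

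**The case against.** A reader might infer that early treatment failures as a class leave the denominator. The documents do not support that. Protocol 6 requires an end-of-treatment visit for fever and for worsening disease, the clearest failures, and Protocol 8.2 has each subject evaluated at the termination visit, whatever the reason for leaving. What remains is that neither place names the GPA. Protocol 8.2 speaks of adverse events, and no visit is stated specifically for lack of efficacy, withdrawn consent or prohibited medication.

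A reader might also infer from the flow charts that the GPA is not collected. It has its own data domain (SAP 5.3) and a listing for all allocated subjects (SAP 9.2.2), and the same SAP visit table also omits end-of-treatment vital signs. This is a gap in documentation.

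Nor is it shown that the result is biased. The scenarios assume that every missing child failed, and the harmful ones use uneven splits. A recovered child has to return within 24 hours and may simply not come, so missing is not always failure. Reasons for termination are summarised by arm (Protocol 10.5), and Protocol 10.1 reports missing counts where appropriate, so differential loss would be partly visible. Visibility does not change the rates or p-value that the plan would report.

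**Conclusion.** The point holds as a risk to one secondary endpoint. The stated rule removes children without a GPA from the success rates and the Fisher test, including any who left for lack of efficacy or prohibited medication, and no planned analysis shows how much that matters. On assumed figures the effect runs from none (equal arms, 6/6 loss, p = 1.00) through loss of significance (p = 0.025 to 0.15) to a spurious result in an extreme split (2/10, p = 0.034). Its direction cannot be stated in advance. The primary log-rank analysis is untouched: SAP 4.2.1 keeps subjects without an event and censors them at 144 hours.

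**What to change.** In SAP 4.2.2 and 4.2.3:

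- Use all subjects allocated to treatment (or the safety sample) as the GPA denominator.
- Count a subject with no GPA as not a success, in particular anyone who terminated for lack of efficacy, worsening or prohibited medication.
- Report as sensitivity analyses the observed-case result and a best/worst-case analysis by arm.
- Tabulate missing GPA by arm and reason.

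In the protocol, state that the GPA is scored at the termination visit for every subject who leaves early, and list it at Visit 2 in the flow charts and the SAP visit table.

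The SAP part costs a few sentences, a changed denominator in table 10.1.4.2.3 and its subgroup tables, and one extra table. It needs no new data and can be settled before database lock. The protocol part helps only children not yet seen; SAP 4.3 already describes the study in the past tense, so it may come too late. The downside is that reported success rates become slightly lower, and a recovered child who does not return counts as a non-success in the main analysis, which is why the best/worst-case result should stand beside it.

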4.2.1 Primary Efficacy Analysis

The primary efficacy variable is the duration (hours) of diarrhea (treatment duration max 5 days). Duration of diarrhea is defined by date ("event" date) of the evacuation of the last diarrheal/watery stool before recovery.

In order to compare the primary efficacy parameter, duration of diarrhea, between the treatment groups, a Kaplan Meier (KM) analysis will be performed. The KM algorithm will be applied to derive the median duration and the 95% confidence intervals for the median, Q1, Q3 and mean duration with Greenwood's estimator of standard deviation of Kaplan-Meier estimator.

The log-rank test will be used to test whether the difference between the duration of diarrhea between two treatment groups is statistically significant, i.e. p-value <0.05.

For duration estimation the date and time of first drug intake will be assumed as start time point and all subjects without "event" will be censored by 6 days (144 hours).

SAS code for the analysis:

PROC LIFETEST DATA = [dataset name] METHOD=KM PLOTS=SURVIVAL OUTSURV=SURV CONFTYPE=LOGLOG ATRISK; TIME [time variable]*[censor variable]; STRATA [arm variable];

RUN;

The "OUTSURV=SURV" statement provides variables that contains the lower and upper limits of the pointwise confidence intervals for the survivor function ("SDF_LCL" and "SDF_UCL"), this confidence intervals should be transformed for tables as follows:

[Lower limit var name] = round(100*(1-SDF_UCL),.1); [Upper limit var name] = round(100*(1-SDF_LCL),.1);

As a first sensitivity analysis, duration of diarrhea will be analyzed by age subgroups as follows:

- Racecadotril + ORS (age subgroup 3 to < 24 month) vs ORS (age subgroup 3 to < 24 month) comparison;
- Racecadotril + ORS (age subgroup >= 2 to <12 years) vs ORS (age subgroup >= 2 to <12 years) comparison;
- Racecadotril + ORS (age subgroup 12 to < 18 years) vs ORS (age subgroup 12 to < 18 years) comparison;

As a second sensitivity analysis, duration of diarrhea will be analyzed by weight/dosing subgroups as follows:

• Racecadotril + ORS (Infants less than 9 kg) vs ORS (Infants less than 9 kg) comparison;

- Racecadotril + ORS (Infants from 9 kg to < 13 kg) vs ORS (Infants from 9 kg to < 13 kg Infants from 9 kg to < 13 kg) comparison;
- Racecadotril + ORS (Children from 13 kg to 27 kg) vs ORS (Children from 13 kg to 27 kg) comparison;
- Racecadotril + ORS (Children from more than 27 kg to 60 kg) vs ORS (Children from more than 27 kg to 60 kg) comparison;
- Racecadotril + ORS (Children or adolescents of 60 kg or higher) vs ORS (Children or adolescents of 60 kg or higher) comparison;

SAS code for the analysis:

```
PROC LIFETEST DATA = [dataset name]

METHOD=KM PLOTS=SURVIVAL

OUTSURV=SURV CONFTYPE=LOGLOG ATRISK;

TIME [time variable]*[censor variable];

STRATA [arm variable];

BY [age subgroup variable];
```

RUN;

```
PROC LIFETEST DATA = [dataset name]
```

METHOD=KM PLOTS=SURVIVAL

OUTSURV=SURV CONFTYPE=LOGLOG ATRISK;

TIME [time variable]*[censor variable];

STRATA [arm variable];

BY [weight/dosing category variable];

RUN;

Description of the Cox regression model analysis is presented in the Section 4.2.3 of the SAP.

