
In children or adolescents of 60 kg or higher: 100 mg capsule 3 times daily
 
Racecadotril will be given three times daily in addition to standard treatment ORS. Other medication to treat diarrhea (see section 7.7) is forbidden.
		
Duration of Treatment: 
The first dose of Racecadotril will be taken on day 1, either the noon or evening dose. The treatment duration lasts until recovery, maximally 5 days, until the morning dose of day 6.
		
Reference Therapy, Dose and Mode of Administration: 
Standard treatment is oral rehydration solution (ORS) according to the registered local label and the instruction of the investigator. The same brand of ORS and the same age-appropriate standardized treatment pattern for the subjects will be applied throughout the trial. No additional reference therapy will be administered together with oral rehydration in the control arm.
		
Criteria for Evaluation: Efficacy: Primary Efficacy Variable: Duration of diarrhea (hours) between the start of treatment until last diarrheal/watery stool before recovery or end of study treatment (treatment duration maximal 5 days). Duration of diarrhea is defined by date and time of the evacuation of the final diarrheal stool derived from the daily diary. Secondary Efficacy Variables: 
 • Number of recovered subjects per treatment group in total and until each individual treatment day. Mean and median time until recovery per treatment group. • Time until recovery, defined by date and time of the evacuation of the first of two consecutive normal stools. • Global Physician Assessment at the end of treatment: 
 ○ 1 = Complete relief of acute diarrhea, ○ 2 = marked improvement of acute diarrhea, ○ 3 = moderate improvement of acute diarrhea, ○ 4 = slight improvement of acute diarrhea, ○ 5 = no change in acute diarrhea, ○ 6 = worsening of acute diarrhea. (Treatment success = GPA score of 1 or 2). 		

Name of Sponsor: Abbott Laboratories GmbH	Name of Finished Product: Hidrased Infants: Granules for Oral Suspension 10 mg Hidrased Children: Granules for Oral Suspension 30 mg Hidrased: 100 mg capsules	Name of Active Ingredient(s): Racecadotril																			

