3 STUDY OBJECTIVES

3.1 Primary Objective(s)

The primary objective is to evaluate the efficacy of Racecadotril in addition to standard treatment oral rehydration solution (ORS) versus ORS alone in infants, children and adolescents (3 months until <18 years) with acute diarrhea measured as duration of diarrhea (hours) between the start of treatment until final diarrheal/watery stool before recovery or end of study treatment (treatment duration maximal 5 days).

Duration of diarrhea is defined by date and time of the evacuation of the final watery/diarrheal stool before recovery derived from the daily diary.

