4 STUDY DESIGN

4.1 Overall Study Design and Plan-Description

This is a controlled, open-label, parallel-group study evaluating the efficacy and safety of Racecadotril in infants, children and adolescents with acute diarrhea. The number of subjects to be screened is 150 in order to enroll 124 subjects for either standard treatment (oral rehydration solution, ORS) alone or ORS plus Racecadotril.

1.5 mg/kg of Racecadotril will be administered, 3 times daily, via the oral route. Study drug intake will start either with the noon or the evening dose on day 1.

In infants less than 9 kg: one 10 mg sachet 3 times daily.

In infants from 9 kg to <13 kg: two 10 mg sachets 3 times daily.

In children from 13 kg to 27 kg: one 30 mg sachet 3 times daily.

In children of more than 27 kg: two 30 mg sachets 3 times daily.

In children or adolescents of 60 kg or higher: 100 mg capsule 3 times daily

Standard treatment is oral rehydration solution (ORS) according to the registered local label and the instruction of the investigator. The same brand of ORS and the same age-appropriate standardized treatment pattern for the subjects will be applied throughout the trial. ORS treatment and dosing will be documented in the CRF.

Screening and Enrolment (Day 1, Visit 1)

Subjects presenting with acute diarrhea will be evaluated for eligibility. They will undergo a physical examination including assessment of dehydration level, vital signs, a review of their medical history and concomitant medication. If the subjects are eligible for the study, demographics, number of stools during the last 24 hours will be assessed as baseline values. The subjects will be randomized to Racecadotril plus ORS or ORS alone. On Day 1 the subject will start with study treatment. The starting dose will either be the noon or the evening dose depending on the timing of Visit 1.

Treatment period (until recovery, maximally 5 days)

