7.8 Treatment Compliance

Drug Accountability

The Investigator is accountable for all clinical drug supplies shipped to his/her study site for the duration of the study. A final accounting of the clinical drug supplies will be required at the completion/termination of the study. The Investigator is required to provide written explanation for any discrepancies.

All used and unused clinical drug supplies will be inventoried and returned to the Sponsor (or an authorized representative) by a designated monitor.

Compliance

Each intake of study drug (Racecadotril) will be recorded in a patient diary and evaluated.

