8.3 Other Assessments

Informed Consent

Voluntary written informed consent must be obtained from one parent(s)/caregiver(s) (or their legally acceptable representative) prior to performing any study-related procedures (see Section 1.3) for all subjects. For subjects < 14 years voluntary verbal assent will be obtained if age and ability allows in addition.

Voluntary written informed assent will be obtained from subjects \geq 14 years of age in addition to parent's written informed consent prior to performing any study-related procedures (see Section 1.3).

Demographic Data

Demographic data (gender, date of birth, race) will be collected for all subjects.

Medical History

Any clinical event, including diagnosis, condition, or surgery, that occurred prior to allocation to treatment, is to be recorded on the Medical History form. In case a clinical event concerns a chronic disorder, which means it started in the past and it is still present at the screening visit, it should also be recorded on the Medical History Form. Examples of these events are diabetes, migraine, and hay fever.

Concomitant Medication

All medication taken by the subject during the study (from signing the informed consent form through post-study follow-up) is to be recorded on the Concomitant Medication form, except for study drug.

Subject Diary

The parent(s)/caregiver(s) have to document date and time of each individual stool of the subject and the stool consistency (watery, normal) of each evacuation continuously. The subject individual stool consistency before start of the diarrhea is defined as normal (e.g. taking into account the age and diet, e.g. breast feeding, of the individual subject). Recording can be stopped after the excretion of two consecutive normal stools.

The date, time and dose of study drug intake as well as the amount ORS and other liquids (e.g. water, milk formula) consumed has to be recorded.

Fever will be measured once daily by the parent(s)/caregiver(s) and documented in the diary including method, time and value.

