6.1.2 Trial Elements

The start time of each intervention will be expressed relative to the first administration of investigational study drug closest to that intervention.

Trial Element	Description of Element	Rule for Start of Element	Rule for End of Element	Planned Duration of Element
Screen	Screening period	Date of Informed Consent	First dose of study treatment	
Racecadotril + ORS	Treatment period	First dose of Racecadotril + ORS	Last dose of Racecadotril + ORS	5 days or less
ORS	Treatment period	First dose of ORS	Last dose of ORS	5 days or less
Follow-up	Safety Follow-Up period	Last dose of study treatment	Investigator's phone call 5-7 days after end of treatment visit	5-7 days

The Trial Elements are presented in the following diagram:

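### The primary clock starts at first drug intake, which falls after randomisation, is not defined by arm, and can be a different event in each arm

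*SAP*

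**What the plan says.** SAP 4.2.1 sets time zero for the primary endpoint: "the date and time of first drug intake will be assumed as start time point". Subjects without an event are censored at 144 h. SAP 4.2.2 analyses time until recovery in the same way. Protocol 3.1 defines the endpoint as "duration of diarrhea (hours) between the start of treatment until final diarrheal/watery stool before recovery or end of study treatment". Neither document measures from randomisation, and neither says which intake counts in which arm.

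The passages that bear on the meaning are these:

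- SAP 6.1.2 starts the treatment period at "First dose of Racecadotril + ORS" in one arm and at "First dose of ORS" in the other.
- Protocol 7.8 identifies study drug with racecadotril: "Each intake of study drug (Racecadotril) will be recorded in a patient diary and evaluated".
- The protocol synopsis (Duration of Treatment) states: "The first dose of Racecadotril will be taken on day 1, either the noon or evening dose". Protocol 4.1 has a similar sentence that names no arm: "The starting dose will either be the noon or the evening dose depending on the timing of Visit 1".
- Protocol 4.1 leaves ORS to the product label and the investigator's instruction, with no slot or start time.
- The diary instruction in Protocol 8.3 covers "The date, time and dose of study drug intake as well as the amount ORS and other liquids". It names a time for study drug but only an amount for ORS.
- The ORS compliance formula in SAP 5.5.1 uses the date and time of the first and last dose.

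**The concern.** Randomisation makes the arms comparable at the moment of allocation. A clock that starts later, at an event that may differ by arm, gives up part of that protection. If racecadotril waits for a slot while ORS is already being taken, the waiting hours drop out of measured duration in the racecadotril arm only, and the curves separate without any drug effect.

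The trial is open-label (Protocol 7.6), so no placebo dose aligns the two clocks. The planned sensitivity analyses (the per-protocol sample, age subgroups and weight subgroups) all use the same origin, so none would reveal the problem. At stake are the primary log-rank test and the main secondary time-to-event comparison.

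**Working it through.** **What the clock can mean.** The control arm receives no racecadotril, so first intake there must be ORS. In the other arm, the first dose of the combination could be the first racecadotril dose, the first ORS intake, or the earlier of the two. If it is the first ORS intake, the arms match. If it is the racecadotril dose, they match only when both are taken at the same time.

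**Plan's own figure.** Protocol 10.8 gives 55 per group, or 62 with 10% drop-out. Freedman's log-rank formula with the 72 h proportions entered as survival proportions gives:

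- ratio = ln(0.842)/ln(0.594) = 0.330
- events = (1.960 + 0.842)² × (1.330/0.670)² ≈ 31.0
- n per group = 31.0/(2 − 0.842 − 0.594) = 54.9, so 55
- 55/0.90 = 61.1, so 62

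The figure reproduces. Whether recovery should be entered as survival is a separate matter. It does not affect what follows, which only takes 62 per arm.

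**Inputs.** The placebo recovery curve in Protocol 10.8 is 18.3%, 35.8%, 59.4%, 76.3% and 80.6% at 24, 50, 72, 96 and 120 h. Censoring is at 144 h and the log-rank test is two-sided at 5%. The offset d, the hours by which the racecadotril clock starts after the control clock, is **not in the documents**; 2 to 8 h is assumed, the same for every subject.

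**Model.** With no true effect, draw T from the placebo curve in both arms. The control arm records T and the racecadotril arm records T − d. The SAP does not say what happens when T − d is negative, so two conventions were run: set to 0, or exclude the subject. Significant results favouring racecadotril (nominal 2.5%):

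| d (h) | Set to 0, linear interpolation (8,000 runs) | Set to 0, piecewise exponential (4,000 runs) | Excluded (4,000 runs) |
|---|---|---|---|
| 0 | 2.7% | 2.9% | 2.6% |
| 2 | 3.5% | 3.4% | 3.5% |
| 4 | 4.8% | 6.0% | 4.0% |
| 6 | 6.7% | 8.0% | 3.8% |
| 8 | 8.6% | not run | 4.3% |

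The columns differ by interpolation rule and simulation error. At 6.0% with 4,000 runs the standard error is √(0.06 × 0.94/4,000) = 0.4 percentage points.

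**Size in hours.** The spurious median difference is about d. At 6 h the simulated medians are 56.3 and 62.3 h. The median difference in the planning study was 64 − 28 = 36 h.

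**Opposite order.** If ORS starts 2, 4 or 6 h after racecadotril, results favouring racecadotril fall to 1.8%, 0.8% and 0.5%.

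**Faster recovery.** If both arms follow the planning racecadotril curve, an 8 h offset gives about 18% with early stools set to 0, but 4.0% with exclusion. On linear interpolation, 46.6% × 8/24 = 15.5% of racecadotril subjects would have passed their last watery stool before the clock started, so the convention decides the result.

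**The case against.** A reader might infer that the endpoint is biased in favour of racecadotril as a matter of fact. The documents do not support that:

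- SAP 6.1.2 does not say which component of the combination starts the clock.
- The noon or evening sentence in Protocol 4.1 follows the randomisation sentence and names no arm, so the slot could apply to both.
- Nothing states that ORS starts at once. It could start before or after the racecadotril dose.
- SAP 3.3 refers to Figure 3-2 for the definition of duration. The figure was not available in the text reviewed and may mark time zero more precisely.

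Nor is it established that the control start time is missing. Protocol 4.1 has ORS treatment and dosing documented in the CRF, and the SAP 5.5.1 formula presupposes a first ORS date and time.

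The largest figures are fragile. They need a long offset in every subject and early stools set to zero; with exclusion the two-sided error in the 1 to 6 h cells on the placebo curve stays at 5.2% to 5.8%. An offset of a few hours is also small beside the 36 h planning difference.

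Finally, the protocol itself measures from start of treatment, so moving to randomisation changes protocol wording as well as the SAP.

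All of this stands, and it limits what can be said about direction and size. It does not supply a definition. Readings with opposite consequences remain open for the time origin of the primary endpoint.

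**Conclusion.** The concern holds as a defect in the definition of time zero. The origin falls after randomisation, is undefined by arm, and can be a different event in each arm. The resulting bias could run either way: toward racecadotril if ORS precedes the slotted dose, away from it if ORS follows. Under an assumed 2 to 8 h later racecadotril start, with no true effect and 62 per arm on the placebo planning curve, the false-positive rate in favour of racecadotril rises from about 2.5% to about 3% to 9% with early stools set to time 0, or about 3% to 5% with those subjects excluded. These figures rest on the assumed offset and on a convention that the SAP does not state. If both arms' clocks in fact start at first ORS intake, this mismatch disappears, but the SAP would need to say so.

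**What to change.** In SAP 4.2.1, make the date and time of randomisation (Visit 1) time zero in both arms, for duration of diarrhea and time until recovery, and count the 144 h censoring from it. If that time was not captured, use one event defined identically in both arms, such as first ORS intake, after checking that its time was recorded in both. State how a last watery stool before time zero is handled. Align the start-of-treatment wording in the protocol's endpoint definition, and keep first-intake time as a sensitivity analysis.

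The cost is a short change to the SAP, matching protocol wording, and a Visit 1 or randomisation time stamp. The documents do not say that a clock time is collected, and SAP 4.3 speaks of the study in the past tense, so availability must be checked first. Reported durations become slightly longer. With a common origin the simulated error is close to nominal (2.6% to 2.9% favouring racecadotril), and the planned 62 per group is unchanged.
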